13.7 Endpoint Analyses

13.7.1 Primary Endpoint Analysis

The primary endpoint is the occurrence of any thromboembolic event or major hemorrhagic complications during the 12-month Evaluation Period.

The Kaplan-Meier method will be used to model the time to the first occurrence of any thromboembolic event or major hemorrhagic complications during the 12-month Evaluation Period following randomization. The survival probabilities of the occurrence of any thromboembolic event or major hemorrhagic complications at the 12 month follow-up along with the corresponding 95% confidence intervals will also be presented. The equality of the survival curves between two randomization groups will be tested by the Log-rank test.

This analysis will include all subjects in the analysis population and account for censored observations. Subjects lost to follow-up, withdrew or discontinued prior to reaching their primary endpoint will be censored at their last visit.

Descriptive statistics such as 25th percentile, median and 75th percentile of time to the first occurrence as well as the 95% confidence intervals around the median time will be presented overall and by randomization groups.

The number and proportion of subjects experiencing occurrence of any thromboembolic event or major hemorrhagic complications will be summarized overall and by two randomization groups at 12 month follow up. The Fisher exact test will be used to compare the proportions between the two randomization groups.

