13. Life expectancy less than 360 days (12 months)
14. Uncontrolled Heart Failure or NYHA Class III or IV heart failure
15. Enrollment in a clinical study evaluating another device or drug, within the past 6 months
16. Unable or unwilling to comply with protocol requirements

Endpoints:

Primary

Composite endpoint represented by the occurrence of any major thromboembolic event (stroke [i.e., ischemic, hemorrhagic or cryptogenic] that is an acute onset of a focal neurologic deficit of presumed vascular origin lasting for ≥ 24 hours or resulting in death) or major hemorrhagic complication (major bleeding) during the 12-month Evaluation Period.

Secondary:

- Minor bleeds
- Hospitalization with any thromboembolic or major hemorrhagic event
- All cause mortality
- QoL (SF-36)
- AF recurrence
- Repeat ablation for AF

Study Duration: 2 years (1 year enrollment period and 1 year follow-up)

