Major hemorrhagic complication	
 • Stroke is an acute onset of a focal neurologic deficit of presumed vascular origin lasting for ≥ 24 hours or resulting in death. 
 ◦ Stroke (i.e., ischemic, hemorrhagic or cryptogenic) occurrence. Stroke is categorized as ischemic or hemorrhagic or cause unknown (based on computed tomographic or magnetic resonance imaging or autopsy). ◦ Fatal stroke is defined as death from any cause within 30 days of stroke. ◦ Severity of stroke will be assessed by modified Rankin score at discharge from hospital and at 3 to 6 months later. • Bleeding (major) is defined by ≥ 1 of the following criteria: 
 ◦ Bleeding associated with reduction in hemoglobin level of at least 2.0 g/L; ◦ leading to transfusion of at least 2 U of blood or packed cells; or ◦ symptomatic bleeding in a critical area or organ such as intraocular, intracranial, intraspinal or intramuscular with compartment syndrome, retroperitoneal bleeding, GI bleeding, intra-articular bleeding, or pericardial bleeding. • Bleeding (life-threatening) if ≥ 1 of the following criteria are met: 
 ◦ fatal, symptomatic intracranial bleed; ◦ reduction in hemoglobin level of at least 5.0 g/L; ◦ transfusion of at least 4 U of blood or packed cells; ◦ associated with hypotension requiring the use of intravenous inotropic agents; or ◦ necessitated surgical intervention.
Minor hemorrhagic event (Minor Bleeds)	Clinical bleeds that do not fulfill the criteria for major bleeds
Paroxysmal AF	Paroxysmal AF is defined as recurrent AF (≥ 2 episodes) that terminates spontaneously within 7 days. Episodes of AF of ≤ 48 h duration that are terminated with electrical or pharmacologic cardioversion should also be classified as paroxysmal AF episodes.
Permanent AF	The term permanent AF is not appropriate in the context of patients undergoing catheter or surgical ablation of AF, as it

Term	Definition
	refers to a group of patients for which a decision has been made not to restore or maintain sinus rhythm by any means, including catheter or surgical ablation. If a patient previously classified as having permanent AF is to undergo catheter or surgical ablation, the AF should be reclassified.

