Persistent AF	Persistent AF is defined as continuous AF that is sustained beyond 7 days. Episodes of AF in which a decision is made to electrically or pharmacologically cardiovert the patient after ≥ 48 h of AF, but prior to 7 days, should also be classified as persistent AF episodes.
Successful Cardiac Ablation	After Cardiac Ablation, no symptomatic or asymptomatic AF recurrence ≥ 30 seconds (without increased or new AADs) following the 3-month blanking period.
Symptomatic AF	Symptom(s) which is/are exhibited by the subject, which make them seek medical attention, and are concurrent with a documented episode by ILR, ECG, TTM, HM, or telemetry recording. Symptoms may include but are not limited to: palpitations, irregular pulse (eg, rapid, racing, pounding, fluttering, bradycardia), dizziness, weakness, chest discomfort, and breathlessness.
Thromboembolic Event	Any documented clinical event due to the embolic occlusion of an artery in the brain or other organs.

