6.0 Study Hypothesis

High risk subjects who have successful cardiac ablation and remain free from AF recurrence for 3 months post ablation procedure can discontinue their OAT without an increased risk of thromboembolic events as compared to those who remain on OAT.

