10.0 Study Endpoints

10.1 Primary Endpoint

The primary endpoint is a composite endpoint represented by the occurrence of any major thromboembolic event (stroke [i.e., ischemic, hemorrhagic or cryptogenic] that is an acute onset of a focal neurologic deficit of presumed vascular origin lasting for ≥ 24 hours or resulting in death) or major hemorrhagic complication (major bleeding) during the 12-month Evaluation Period.

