13.0 Statistical Analysis Plan

13.1 Study Objective

The objective of this study is to assess whether the patients who discontinued OAT after a successful AF ablation are not inferior to the group of patients who continued OAT after a successful AF ablation in terms of the composite endpoint of all ischemic and hemorrhagic events.

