13.2 Primary Endpoint

The primary endpoint is a composite endpoint represented by the occurrence of any major thromboembolic event (stroke [i.e., ischemic, hemorrhagic or cryptogenic] that is an acute onset of a focal neurologic deficit of presumed vascular origin lasting for ≥ 24 hours or resulting in death) or major hemorrhagic complication (major bleeding) during the 12-month Evaluation Period.

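### Section 13.7.1 analyses a wider thromboembolic endpoint than Sections 3.0, 10.1 and 13.2 define, and all its outputs pool thromboembolic events with major bleeding

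*Combined protocol and SAP*

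**What the plan says.** Section 13.2 gives the thromboembolic part of the primary endpoint as "occurrence of any major thromboembolic event (stroke [i.e., ischemic, hemorrhagic or cryptogenic", and the sentence closes the bracket with a clinical threshold. The same threshold stands in 3.0 and 10.1: the stroke "is an acute onset of a focal neurologic deficit of presumed vascular origin lasting for ≥ 24 hours or resulting in death". The other part, in 10.1, is "or major hemorrhagic complication (major bleeding) during the 12-month Evaluation Period".

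Section 13.7.1 opens its analysis with "The primary endpoint is the occurrence of any thromboembolic event or major hemorrhagic complications during the 12-month Evaluation Period". It uses that phrase again for the Kaplan-Meier analysis, the 12-month survival probabilities, and the counts and proportions compared by the Fisher exact test. It mentions neither stroke nor 24 hours.

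Table 2 in Section 4.0 has an entry for thromboembolic event: "Any documented clinical event due to the embolic occlusion of an artery in the brain or other organs". Under its entry for major hemorrhagic complication it lists "Stroke (i.e., ischemic, hemorrhagic or cryptogenic) occurrence" alongside major bleeding.

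Section 13.1 words the objective differently again: "in terms of the composite endpoint of all ischemic and hemorrhagic events". The hypothesis in Section 6.0 is that suitable subjects "can discontinue their OAT without an increased risk of thromboembolic events as compared to those who remain on OAT". Section 13.3 sets 50 subjects per arm and states that the pilot is not powered for inference.

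**The concern.** There are two separate problems.

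**Definition.** The section that governs the programming states the endpoint in words that Table 2 defines more broadly than 10.1 and 13.2 do. Whoever builds the event variable must choose between them, and in an unblinded trial that choice should be settled before outcomes are seen. It is also unclear to which part of the composite a stroke belongs. Table 2 files every stroke, ischemic included, under the hemorrhagic heading. Sections 10.1 and 13.2 place every stroke, hemorrhagic included, in the thromboembolic part and equate the hemorrhagic part with major bleeding.

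**Pooling.** Section 5.3 expects opposite main risks in the two arms: bleeding and hemorrhagic stroke on OAT, thromboembolism off it. When components move in opposite directions, similar composite rates can conceal a thromboembolic excess off OAT. No output in 13.7.1 would show it, although the hypothesis is about exactly that component.

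**Working it through.** The plan has no figure to reproduce here: 13.3 gives the sample size without alpha, power, effect size or margin. The check is a comparison of texts, followed by simple illustrations.

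**Step 1: what counts under each text.** The last column applies Table 2 to both terms in 13.7.1.

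| Event | 3.0, 10.1, 13.2 | 13.7.1 with Table 2 |
|---|---|---|
| Ischemic or cryptogenic stroke, 24 hours or more, or fatal | Yes, thromboembolic part | Yes, through the stroke entry under major hemorrhagic complication |
| Hemorrhagic stroke | Yes, thromboembolic part | Yes, same entry |
| Other major bleeding | Yes | Yes |
| Embolic brain event under 24 hours, not fatal | No | Yes |
| Systemic embolus | No | Yes |

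Read this way, 13.7.1 contains everything in 13.2 and adds the last two rows.

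**Step 2: effect on the count.** Each reclassified subject moves an arm by 1/50 = 2 percentage points. As a hypothetical example, let one arm have one stroke of at least 24 hours, one systemic embolus and one embolic brain event under 24 hours, in three subjects. The primary count is 1/50 = 2% under 13.2 and 3/50 = 6% under 13.7.1 with Table 2.

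**Step 3: effect of pooling.** Suppose 3 ischemic strokes of embolic origin off OAT and 3 major bleeds on OAT, so that the definition is not in play. The example is chosen to cancel exactly.
- Composite: 3/50 against 3/50, difference 0, Fisher p = 1.00.
- Thromboembolic events only: 3/50 against 0/50, difference 6 points, Fisher p = 0.24.

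Neither comparison supports a test. What is lost is the descriptive contrast.

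**Step 4: the protocol's background figures.** Section 5.1 gives an absolute stroke reduction on warfarin of 2.7% per year (primary prevention) or 8.4% (secondary), and 1.2% per year more major bleeding. Netting these gives 2.7 − 1.2 = 1.5 points and 8.4 − 1.2 = 7.2 points. This assumes that the stroke figures are essentially thromboembolic and that all of them apply after successful ablation. They come from general AF, and 5.2 notes very few thrombotic events after success, so they show the direction of the effect and not its expected size.

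**Step 5: which splits are planned elsewhere.** Section 13.7.2.2 summarises type of event by arm for hospitalisations. Section 13.7.2.3 summarises causes of death by arm. Together they leave out non-fatal events without hospitalisation.

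**The case against.** The best defence is that 13.7.1 is shorthand. Three sections carry the full definition, one of them in the same analysis plan, and 8.2 uses a similar short phrase. That may well be the intent. But 13.7.1 is worded as a definition, repeats the phrase throughout its analyses, and uses a term that the protocol's own glossary defines more widely. The defence makes the correction easy; it does not remove the need for it.

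On pooling, a net composite fits the objective and design in 7.0, 8.1, 8.2 and 13.1, so the choice of primary endpoint is not at fault. Sections 13.7.2.2 and 13.7.2.3 will separate many of the serious events; because Table 2 scores stroke severity at hospital discharge, most strokes may be covered. The remaining gap is real but limited.

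A reader might also infer that neither definition contains the other, so that a cryptogenic stroke could drop out of 13.7.1 altogether. That needs a mixed reading: Table 2 for the thromboembolic term, but 13.2's equation with major bleeding for the hemorrhagic term. Read consistently, 13.7.1 either equals 13.2 or contains it.

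**Conclusion.** Both parts hold. Sections 3.0, 10.1 and 13.2 give one primary endpoint, and 13.7.1 read with Table 2 gives a wider one that adds systemic emboli and embolic brain events under 24 hours. The assignment of stroke to a component is inconsistent between Table 2 and 10.1/13.2. No primary output isolates the events named in the hypothesis.

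The size of the definitional effect is unknown and could be zero, since the documents give no rate for the added events. The masking examples are hypothetical. A reader might infer that the study's conclusion would be reversed or its power lost; 13.3 disclaims inference, so the documents do not support that. The point should be put right because a pilot of this kind rests on its descriptive counts, and these should have one meaning.

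**What to change.** **1. One definition.** Make 13.1 and 13.7.1 use the 10.1/13.2 definition. State that the Table 2 entry for thromboembolic event is not the primary-endpoint term. In Table 2, list stroke separately from major bleeding. The short phrase in 8.2 can be aligned at the same time.

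**2. One descriptive table.** Keep the composite as primary. Add, by arm, each subject's first composite event by type: ischemic stroke, cryptogenic stroke, hemorrhagic stroke, other major bleeding. Give counts and exact binomial 95% intervals, the method already named in 13.7.2. Hemorrhagic stroke has its own line, with a note that 10.1 and 13.2 count it within stroke. Systemic emboli and embolic events under 24 hours go on a separate line outside the composite.

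**3. The Section 6.0 hypothesis.** Report descriptively (a) ischemic plus cryptogenic stroke and (b) the same plus systemic emboli and embolic events under 24 hours, counting each subject once. Showing both avoids resting the hypothesis on a group that omits systemic emboli. State that neither is confirmatory.

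The cost is some wording and one extra table. The intervals will be wide: for 0/50 the exact upper limit is 1 − 0.025^(1/50) = 7.1%, and 3/50 gives 1.25% to 16.55%.

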9.6 Subject Disposition

Evaluable Subjects

- **Enrolled Subjects:** subjects who sign the study's informed consent form
- **Randomized Subjects:** subject who remain free from arrhythmia recurrence after signing the study ICF and are randomized into one of the study arms (OAT withdrawal or OAT).
- **Completed Subjects:** enrolled subjects who have not been discontinued, withdrawn or lost-to-follow-up from the study prior to the final (12 month) study visit.
- **Lost to Follow-up Subjects:** subjects who are enrolled and randomized, but contact is lost after most recent follow-up visit (despite 3 documented attempts to contact the subject, two (2) by documented telephone calls, and one (1) written attempt sent by registered mail).
- **Discontinued:** Subjects that have arrhythmia recurrence at any time during the Evaluation Period will be discontinued. Discontinued subjects are exited from the study prior to completion of all follow-up visits; however, they will remain in the analysis cohort until the time at which they are discontinued from the study.
- **Withdrawn Subjects:** Subjects may be withdrawn for reasons stated below in Section 9.7. Withdrawn subjects are exited from the study prior to completion of all follow-up visits; however, they will remain in the analysis cohort until the time at which they are withdrawn.

Non-Evaluable Subjects

- **Excluded:** Subjects found to not meet one of the study inclusion/exclusion criteria after the being enrolled.

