9.7 Subject Withdrawal

The investigator may remove a subject from the study for any of the following reasons: withdrawal is in the subject's best interest, subject preference, concurrent illness, noncompliance, or any other situation the investigator deems a compromise to the integrity of the study. Subjects will be informed prior to study entry that they are free to withdraw from the study at any time and for any reason, without prejudice to his or her future medical care by the physician or the institution.

If a subject is removed from the study, the date and reason for withdrawal will be recorded on the appropriate electronic case report form (eCRF). If the subject is withdrawn due to an adverse event (AE) or serious adverse event (SAE), the Investigator must comply with all reporting requirements described in Section 12 and must follow the subject until the AE/SAE has resolved or stabilized.

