11.2 Medication Management

11.2.1 OAT Management

Prior to enrollment in the OAT Pilot Study, subjects' OAT should be administered at the discretion of the investigator and in accordance with current AF management guidelines.^{6, 30-32} Subjects should continue their physician-prescribed regimen for OAT until they are enrolled in the OAT Pilot Study. Subjects randomized to the OAT (Control) Group should continue their current OAT regimen; however, changes are allowed per the investigator's discretion (i.e., from one type of OAT to another) during the Evaluation Period. All commercially approved OAT medications may be prescribed to subjects in the OAT (Control) Group. Subjects in the OAT Withdrawal (Test) Group who resume OAT during the Evaluation Period, regardless of the reason, will be discontinued from the study at the time when OAT therapy is resumed.

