11.4.3 Unscheduled Visits

If a subject returns for visit outside of the protocol-defined visit windows provided in the Study Visits Section (11.4.1) of this protocol, the visit will be considered "unscheduled". If the unscheduled visit is for any purpose other than a repeat ablation procedure, an unscheduled visit CRF must be completed and the subject must also return for their next scheduled study visit. A list of the requested/recommended assessments that should be performed during the unscheduled visits is included in Table 3.0. If the unscheduled visit is for arrhythmia recurrence, the subject must be discontinued from the study as previously indicated in the Subject Disposition Section (9.6) of this protocol. All appropriate forms (eg, Final Status Form) must be completed for subjects that are discontinued due to arrhythmia recurrence within the Evaluation Period.

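### Section 13.7.1 censors discontinued and withdrawn subjects at their last visit, Section 9.6 counts them until exit; for exits between visits the 13.7.1 rule slightly inflates the 12-month Kaplan-Meier risk

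*Combined protocol and SAP*

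**What the plan says.** The primary analysis in Section 13.7.1 is a Kaplan-Meier estimate of time to first thromboembolic or major hemorrhagic event over 12 months, with a log-rank test. One censoring rule covers three groups: "Subjects lost to follow-up, withdrew or discontinued prior to reaching their primary endpoint will be censored at their last visit".

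Section 9.6 sets the end of observation differently. For discontinued subjects, "they will remain in the analysis cohort until the time at which they are discontinued from the study". For withdrawn subjects, "they will remain in the analysis cohort until the time at which they are withdrawn". Lost-to-follow-up subjects are those for whom "contact is lost after most recent follow-up visit".

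Exits can occur on any day:

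- In both arms: "Subjects that have arrhythmia recurrence at any time during the Evaluation Period will be discontinued" (Section 9.6).
- In the test arm only: a subject who resumes OAT "will be discontinued from the study at the time when OAT therapy is resumed" (Section 11.2.1).
- In both arms: repeat ablation (Section 11.3).

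Table 3 places the scheduled follow-up visits at 3, 6 and 12 months and also has a column for unscheduled visits. Section 13.7.1 does not say whether an unscheduled visit can be the last visit.

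On exit dates, Section 9.7 requires the date and reason to be entered on the eCRF when a subject is removed. For AF-recurrence exits, Section 11.4.3 requires closing forms such as the Final Status Form, but does not name a date field.

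**The concern.** Take a subject who leaves event-free in month 11 and whose last visit was at month 6. Under Section 9.6 this subject contributes 11 months. Under Section 13.7.1 the subject contributes 6. A subject with an event in month 11 is counted at month 11 under both rules. Event-free time is removed while events are kept, so the risk sets are too small when later events occur and the estimated risk is too high. A subject who exits before the 3-month visit could contribute no follow-up at all.

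Two things are at stake. Analysts who follow different sections would report different primary estimates. Also, the study disclaims power for inference (Section 13.3), so the estimates and their intervals are its main product, and these are what the rule shifts. Test subjects have an additional cause of exit, and Section 11.4.2 strongly recommends continuous monitoring for the off-OAT cohort, so more exits in that arm are plausible. The shift would then count against withdrawal of OAT.

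**Working it through.** The plan gives no figure to reproduce: the 100 subjects (50:50) in Section 13.3 come without a derivation, and no exit rate is stated. The check therefore measures the difference between the two rules.

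**Inputs from the documents.** Visits at 0.25, 0.5 and 1.0 year (Table 3), so the intervals are w = 0.25, 0.25 and 0.5; 50 per arm (Section 13.3); background rates from fewer than 2 to more than 10 strokes per 100 patient-years without antithrombotic therapy, and 1.5 to 4.2 major hemorrhages per 100 patient-years by age (Section 5.1).

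**Assumptions.** A proportion q of subjects exits by 12 months, at a constant rate λ = −ln(1−q), independently of the event. All exits fall between visits unless stated.

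**Step 1: a small example.** There are 50 subjects, one event at month 8, and 10 event-free exits at month 9 with the last visit at month 6. With exit-date censoring, 50 are at risk at month 8: 1/50 = 2.0%. With last-visit censoring, 40 are at risk: 1/40 = 2.5%.

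**Step 2: a general formula.** When events are rare, a subject is in the risk set at time t within an interval ending at v only if there is no exit before v. The apparent hazard is then the true hazard times exp(λ(v−t)). Integrating over the three intervals gives the inflation of the cumulative hazard, and for small risks approximately that of the 12-month risk:

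inflation = [2(exp(0.25λ) − 1) + (exp(0.5λ) − 1)] / λ

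| q (assumed) | λ | numerator | inflation |
|---|---|---|---|
| 10% | 0.1054 | 2(0.0267) + 0.0541 = 0.1075 | 1.020 |
| 15% | 0.1625 | 2(0.0415) + 0.0847 = 0.1676 | 1.031 |
| 25% | 0.2877 | 2(0.0746) + 0.1547 = 0.3038 | 1.056 |
| 40% | 0.5108 | 2(0.1362) + 0.2910 = 0.5634 | 1.103 |
| 50% | 0.6931 | 2(0.1892) + 0.4142 = 0.7926 | 1.144 |

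**Step 3: simulation without the rare-event approximation.**

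- True 12-month risk 2.96% (4,000,000 subjects per setting): exit-date censoring returns 2.95–2.96%. Last-visit censoring gives 3.01%, 3.12% and 3.37% at 10%, 25% and 50% exits, ratios of 1.020, 1.055 and 1.141. Follow-up lost is 1.9%, 5.1% and 11.6%.
- Across event rates of 1.5 to 10 per 100 patient-years the ratios hardly change (1.13 to 1.14 at 50% exits).
- True risk about 4% (2,000,000 subjects per setting): last-visit censoring gives 4.10%, 4.20% and 4.39% at 15%, 25% and 40% exits.

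**Step 4: exits that coincide with a counted visit.** If half do, the inflation at 10%, 25% and 50% exits falls to 1.0%, 2.6% and 6.3%. If all do, it is zero.

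**Step 5: between arms, 50 + 50, equal true hazards (4,000 replicates).**

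| Exits, test vs control | Event rate per 100 patient-years | Mean risk difference, last-visit rule | SD of the difference |
|---|---|---|---|
| 40% vs 20% | 3 | +0.14 points | 4.1 points |
| 50% vs 10% | 3 | +0.39 points | 4.1 points |
| 40% vs 20% | 10 | +0.57 points | 7.0 points |
| 50% vs 10% | 10 | +1.07 points | 7.1 points |

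With exit-date censoring the mean difference is within 0.04 points of zero in all four settings. For 50% vs 10%, log-rank rejection goes from 2.2% to 2.9% at the lower rate and from 5.2% to 5.6% at the higher.

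**The case against.** The strongest reply is that Section 13.7.1 says last visit, not last scheduled visit. Under Section 11.4.3, "If the unscheduled visit is for arrhythmia recurrence, the subject must be discontinued from the study", and the unscheduled-visit column of Table 3 includes medical history, ECG, medications and adverse events. If recurrence is found at a counted visit, exit and last visit coincide and nothing is lost. This stands as a limit on size. A reader might infer that every month-11 exit is cut back to month 6; the documents do not support that. Nor do they rule it out: the term is undefined, OAT can be resumed between visits, and Section 11.4.3 exempts repeat-ablation visits from the unscheduled-visit form.

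The second reply is that the effect is negligible here. With 50 per arm one event is 2 percentage points, and at a 4% risk the standard error of the difference is about √(2 × 0.04 × 0.96 / 50) = 3.9 points. The Fisher comparison of proportions in Section 13.7.1 uses no censoring dates and is unaffected. This also stands: the matter is one of specification and does not threaten the trial.

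Third, a reader might infer that the arm with more exits always carries the larger bias. That holds for relative inflation when exit timing is similar, and for absolute bias when event rates are similar. With unequal rates it can fail: 1 event per 100 patient-years with 50% exits gives +0.14 points, while 5 per 100 with 25% exits gives +0.27.

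Fourth, exits follow AF recurrence or resumption of OAT and may be related to risk, so exit-date censoring does not make the estimate unbiased. That is correct. The claim here is only about the gap between the two rules.

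Finally, for lost-to-follow-up subjects the last-visit rule already agrees with Section 9.6. The conflict concerns only discontinued and withdrawn subjects.

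**Conclusion.** The point holds in a limited form. For discontinued and withdrawn subjects, Sections 13.7.1 and 9.6 set different censoring dates whenever the exit falls between visits, and the 13.7.1 rule then biases the 12-month Kaplan-Meier risk upward relative to exit-date censoring. If all exits fall between visits, the relative inflation is about 2–3% at 10–15% exits, 5% at 25% and 10% at 40%. It shrinks to zero as exits coincide with counted visits.

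The direction follows from the rule itself. The size rests on assumed exit rates, a constant exit rate, and exits independent of events. The bias need not cancel between arms, because one cause of exit applies only to the test arm. At similar event rates it is larger in the arm with more exits, but the documents do not show which arm that will be.

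The results do not support a reading that this invalidates the comparison or materially changes the log-rank test. It is an avoidable inconsistency in the primary analysis that should be settled before the data are analysed.

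**What to change.** Amend the censoring sentence in Section 13.7.1 as follows:

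- Discontinued and withdrawn subjects without a primary event are censored at the recorded date of exit, in line with Section 9.6.
- Lost-to-follow-up subjects remain censored at the last visit or contact with known event status. State whether an unscheduled visit counts.

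Then confirm that the Final Status Form records the exit date for AF-recurrence discontinuations. Section 9.7 already requires a date for subjects who are removed, but Section 11.4.3 does not say so for this group.

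The cost is one revised SAP sentence and a check of one form, with no new visits or assessments if the date is already captured. The change does not deal with informative censoring or with events after exit, which need separate attention.
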